Secondary Effectiveness Objective	
 • RAP treatment effectiveness: The secondary effectiveness objective is to demonstrate the improvement in the appearance of cellulite as determined by the study participants selecting “Agree” or “Strongly Agree” as answers to the Participant Satisfaction Survey (Assessment 3): when comparing side-by-side before and after photographs.
Test Device	ZELTIQ Aesthetics, Inc. Rapid Acoustic Pulse (RAP) device.
Treatment	
Each cellulite treatment session will consist of RAP treatment [REDACTED] to bilateral thigh and/or buttock areas using the same treatment settings for both sides.
 
The participants will have three (3) separate cellulite treatment sessions. The second treatment session will occur four (4) weeks post the initial treatment. The third treatment session will occur twelve (12) weeks post the second treatment.

Control	For each cellulite treatment area, the pre-treatment photos of the thighs and/or buttocks area will serve as a control.
Study Design	Non-significant risk, single-site, prospective clinical trial.
Planned Number of Sites / Countries	One clinical trial site located in the United States.

Planned Duration of Participant Engagement	Up to seventy-two (72) weeks [REDACTED]
Planned Number of Participants/ Treatment Areas	Up to 15 participants [REDACTED] (total of two thighs and/or buttocks per participant) The clinical site (CS) will recruit up to 15 participants. This will provide a total of up to thirty treatment areas.
Primary Effectiveness Endpoint	
 Effectiveness Endpoint: An Independent Photo Review (IPR) panel will be asked to identify the 12-weeks post final treatment photographs from randomly placed side-by-side before and after photographs, for all participants who meet all the inclusion criteria and none of the exclusion criteria and complete the 12-weeks follow-up visit. The number of before and after photos correctly identified by at least 2 of 3 blinded reviewers from the IPR panel will be recorded. [REDACTED]
Primary Safety Endpoint	
 RAP treatment safety endpoint: To demonstrate safety through the absence of unexpected adverse events (UAEs) and serious adverse events (SAEs) directly attributable to the RAP device or treatments.

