	
exclusion criteria and complete the 12-week follow-up visit. The number of before and after photos correctly identified by at least 2 of 3 blinded reviewers from the IPR panel will be recorded.
 
[REDACTED]

RAP treatment safety: The primary objective is to evaluate the safety of the RAP device for cellulite treatments.
	
RAP treatment safety endpoint: The numbers and proportions of participants with AEs, SAEs, ADEs, SADEs, and unanticipated AEs or ADEs will be summarized.
 
RAP treatment safety: The safety objective is to evaluate the safety of the RAP (Rapid Acoustic Pulse) device for cellulite treatments through the monitoring of the incidence of adverse events (AEs) and adverse device effects (ADEs); serious adverse events (SAEs) and SADEs (serious adverse device effects) and pain assessments.

Secondary Objectives	Secondary Outcome Endpoints

RAP treatment effectiveness: The secondary objective is to demonstrate the improvement in the appearance of cellulite as determined by the study participants.
	
For all participants who meet all inclusion criteria and none of the exclusion criteria and are followed up at the 12-week timepoint post final treatment,
 
[REDACTED]
 
[REDACTED]
 
In comparison to the pre-treatment photo, the 12-week photograph of the treatment area appears improved.

STUDY DESIGN

This is a non-significant risk, single-center, prospective trial for safety, and effectiveness using ZELTIQ Aesthetics, Inc.'s RAP device for the improvement in the appearance of cellulite performed at 1 clinical research site in the United States.

Up to fifteen (15) healthy participants between the age of 18-50 will be enrolled in this study.

Participants who sign the informed consent form and meet all the eligibility criteria will be enrolled in the study. Each participant will undergo acoustic rapid pulse (RAP) treatments on both of their thighs and/or buttocks.

Total study duration is anticipated to be at or less than 72 weeks from the first participant visit to the last participant observation visit. A total of up to 7 visits are planned for this study [REDACTED].

Selection of Study Population

The clinical study can fulfill its objectives only if appropriate participants are enrolled.

The following criteria are designed to select participants for whom protocol requirements are considered appropriate.

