The investigational site will provide direct access to all trial-related site's source data/documents, and reports for the purpose of monitoring and auditing by ZELTIQ Aesthetics, Inc. or designee, and inspection by local and regulatory authorities (as appropriate).

The investigational site will have established standard operating procedures (SOPs) for quality management. Data will be evaluated for compliance with the protocol and accuracy in relation to source documents. The study will be conducted in accordance with procedures identified in the protocol.

The data and any research conducted will be controlled by ZELTIQ Aesthetics, Inc.

STUDY RESULTS/ANALYSIS

Sample Size Determination: Up to fifteen (15) participants will be enrolled and treated in this study. The sample size is based on clinical and practical exploratory considerations and not a formal statistical power.

Demographics and Baseline Characteristics: Demographic and baseline characteristics will include age, sex, ethnicity, race, gender identity, height, and weight, Fitzpatrick Skin Type, and Cellulite Dimple assessment of bilateral posterior thighs and/or buttocks.

Study Analysis Populations: The Full Analysis Set (FAS) will include all participants who meet all the inclusion and none of the exclusion criteria, received assigned three treatments with the device and completed the 12-week, follow-up visits per the protocol. The FAS will be treated as the primary analysis set.

Effectiveness Parameter Analysis: Descriptive statistics will be performed on the population per protocol, all participants completing the study without major protocol deviations. Descriptive statistics (i.e., mean, standard deviation, etc.) will be provided for all continuous variables, percentages and frequencies for all categorical variables collected in this study.

Summary tables will be used to present population characteristics at Baseline. For categorical parameters, the number and percentage of participants in each category will be presented. The denominator for percentage will be based on the number of participants appropriate for the purpose of analysis. For continuous parameters, descriptive statistics will include n (number of participants), mean, standard deviation, median, and range. No imputation will be used to account for missing data. No processing for outliers will be performed. Data will be presented as reported on the CRF. [REDACTED]

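### In the visible text, the participant endpoint discloses which photograph is the 12-week one, so agreement alone cannot separate seen from expected improvement

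*Combined protocol and SAP*

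**What the plan says.** The objectives and endpoints table (Protocol 2021-06 Study Objectives and Endpoints) states: "The secondary objective is to demonstrate the improvement in the appearance of cellulite as determined by the study participants". The Study Synopsis lists this as an effectiveness objective. It is measured by answers of Agree or Strongly Agree on the Participant Satisfaction Survey (Assessment 3), given "when comparing side-by-side before and after photographs". The only item wording left visible, in the same table, is "In comparison to the pre-treatment photo, the 12-week photograph of the treatment area appears improved".

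The primary endpoint uses a different procedure. The review panel must "identify the 12-weeks post final treatment photographs from randomly placed side-by-side before and after photographs", and the scoring rule is: "The number of before and after photos correctly identified by at least 2 of 3 blinded reviewers from the IPR panel will be recorded".

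There is no sham or untreated arm. Under Control, the Synopsis says that for each treatment area "the pre-treatment photos of the thighs and/or buttocks area will serve as a control". Study Design adds: "Each participant will undergo acoustic rapid pulse (RAP) treatments on both of their thighs and/or buttocks". Under Study Results/Analysis the effectiveness analysis is descriptive, and on size the plan says: "The sample size is based on clinical and practical exploratory considerations and not a formal statistical power".

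**The concern.** A participant cannot answer the visible item without knowing which photograph came first, and the item itself offers the favourable answer. Respondents sought treatment and have had three sessions by then. Expectation and a tendency to agree can therefore raise the Agree/Strongly Agree rate, and a single-arm design has no comparison group from which to estimate and remove that effect.

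The protocol guards against this for the physician panel, where blinded reviewers pick from randomly placed pairs and guessing has a known success rate. The agreement item has no such reference rate. What is at stake is the wording of the conclusion: a high agreement rate could be reported as improvement demonstrated by participants when part of it comes from knowing which picture is the later one.

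**Working it through.** **Plan's own figures.** The visible plan gives no alpha, power, null rate or success threshold for this endpoint, so there is no design figure to reproduce. The background percentages from the earlier pivotal study (Introduction) fit whole counts out of its 56 analysed participants: 52/56 = 92.9% positive satisfaction and 54/56 = 96.4% correct identification.

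**Step 1: possible inflation.** Let t be the true share of participants who see an improvement, and b the share of the remainder who agree anyway. Assuming that everyone who sees an improvement agrees, observed rate = t + b(1 − t) and inflation = b(1 − t). The documents give no value for b, so 20% to 50% is an assumption. Two values of t are used: 60%, which is an assumption, and 90.9%, the share of treated locations graded as improved on the GAIS in the pivotal study.

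| t | b = 0.20 | b = 0.50 | Inflation |
|---|---|---|---|
| 0.60 | 0.60 + 0.20 × 0.40 = 0.680 | 0.60 + 0.50 × 0.40 = 0.800 | 8 to 20 points |
| 0.909 | 0.909 + 0.20 × 0.091 = 0.927 | 0.909 + 0.50 × 0.091 = 0.955 | about 2 to 5 points |

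At n = 15 one participant is 1/15 = 6.7 points. The first range is therefore about one to three participants, and the second is less than one.

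**Step 2: the missing reference rate.** Suppose no change were visible and each of 15 participants agreed with probability a. The exact binomial probability that 12 or more agree is:

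| a | P(12 or more of 15) |
|---|---|
| 0.5 | 0.018 |
| 0.6 | 0.09 |
| 0.7 | 0.30 |
| 0.8 | 0.65 |
| 0.9 | 0.94 |

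For a = 0.5 this is (455 + 105 + 15 + 1)/32,768 = 576/32,768 = 0.018. The cut-off of 12 is illustrative (one-sided 0.025) and is not in the plan. Because a is unknown for the agreement item, 12 of 15 could be strong evidence or none.

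**Step 3: the same count from a masked choice.** A forced choice from an unlabelled pair in random order fixes the reference at 0.5. With one choice per participant, 12 or more of 15 then has probability 0.018 under guessing. If the true rate of choosing the 12-week image were 92.9% (borrowed from the pivotal satisfaction result as an assumption), that count would be reached with probability 0.98.

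**Step 4: two areas per participant.** The 0.5 reference applies to each area. If the left/right order is drawn independently for each area, choosing the 12-week image for both has probability 0.5 × 0.5 = 0.25 under guessing. A participant-level rate based on both areas should be read against 25%, not 50%.

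**The case against.** The strongest reply has four parts.

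- **Redaction.** Text directly before the visible item is redacted, as are parts of the Synopsis endpoint and of the Visit 5 procedures, and the survey is not reproduced. A masked step could be hidden there. This stands: a reader might infer that participants are given no masking at all, but the documents support only that none is visible. The visible item would still disclose the order when it is answered.
- **The endpoint is participant opinion.** The instrument is already called a satisfaction survey, and agreement measures what participants think. This also stands. A reader might infer that the agreement rate shows nothing about improvement. That goes too far, because it is a valid report of opinion. It falls short only of an effectiveness objective worded as demonstrating improvement.
- **The primary endpoint covers visibility.** Blinded reviewers already test whether change can be seen without knowing the order, and the study is small and descriptive. This limits the weight of the point, but it does not supply the participants' own masked view, which the secondary objective claims.
- **The size is assumed.** A reader might take 8 to 20 points as the expected bias. The documents do not support that, because t = 60% has no source in them. The alternative of 90.9% is imperfect too: it counts locations, follows a single session in another study, and the masking of that grading is not clear. In the pivotal study satisfaction (92.9%) did not exceed blinded identification (96.4%), though nothing shows that the 92.9% came from this item.

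It might also be inferred that the sponsor's presence sways the survey answers. The protocol places the sponsor's team at treatment and photography, but nowhere visible at the survey.

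**Conclusion.** The point holds in a limited form. As far as the visible text shows, the secondary effectiveness objective rests on agreement with a positively worded item that tells treated, unblinded participants which photograph is the later one. In a single-arm study that rate cannot by itself distinguish seen from expected improvement.

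The amount of inflation cannot be established from the documents. It runs from about 2 points to 20 points across the two values of t and the assumed 20% to 50% for b. The conclusion also assumes that no masked step lies under the redactions. The blinded primary endpoint is unaffected. This is a cheap improvement to a secondary endpoint in an exploratory study, not a threat to the trial.

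**What to change.** First, the sponsor should confirm whether a masked participant step already exists in the redacted text. If it does, nothing more is needed than to base the improvement statement on it.

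If it does not, add the following at Visit 5, before Assessment 3:

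1. For each treatment area, show the pre-treatment and 12-week photographs unlabelled. Take the left/right order from a simple random list made for this purpose and drawn independently for each area. It should not depend on the panel's pairs, which the documents do not show to be ready by Visit 5.
2. Ask which photograph looks better, as a forced left/right choice, so that the 50% reference holds for each area. If a no-difference answer is offered, count it as not improved and apply the 50% reference only to those who choose a side.
3. Report results per area. Count a participant as improved only if the 12-week image is chosen for both areas, and read that rate against 25%.
4. Then give Assessment 3 unchanged.

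Base the statement about improvement as determined by participants on the masked choice, and report the Agree/Strongly Agree rate as satisfaction.

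The cost is one extra question per area, using photographs already scheduled. The masked rate may be less favourable. Asking for a choice first may influence the survey answers. Masking is only partial if participants recognise their own images.

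If the question is not added, the minimum change is to describe the agreement rate as unmasked participant satisfaction and not as demonstrated improvement.

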**Visit 6 Follow Up Visit 26- Weeks Post 3rd Treatment (+/- 14 days)**

- Weight
- Review concomitant medication
- Adverse Event evaluation
- Review Participant Pre and Post Treatment Instructions
- 2D Photos of the treatment area

**Visit 7 Follow Up Visit 52- Weeks Post 3rdTreatment (+/- 14 days)**

[figure not shown]
- Weight
- Review concomitant medication
- Adverse Event evaluation
- 2D Photos of the treatment area

* Local, national, or federal holidays may occur during the timeframe of this study, which may alter the follow up dates.

PHOTOGRAPHY

Baseline photographs will be taken under standardized lighting and equipment settings.

UNSCHEDULED VISITS

An unscheduled visit may be performed at any time during the study at the participant's request or as deemed necessary by the study investigator. The date and reason for the visit will be recorded in the source document.

[figure not shown]
PARTICIPANT WITHDRAWAL AND EARLY TERMINATION

[figure not shown]
Participants may withdraw from the study at any time at their own request or withdrawn from at any time at the discretion of the Investigator for safety, behavioral, or administrative reasons. The Investigator should inquire about reason for withdrawal, request the participant to return for a final visit, and follow up with any unresolved adverse events. The Investigator should notify the Sponsor of any participants withdrawal or discontinuance.

RISKS AND BENEFITS

Clinical Benefit

There is no clinical benefit in this study. The participant may experience an improvement in the aesthetic appearance of the treated areas.

Risk Mitigations

The Investigator in this clinical study has been invited to participate in this study based on his/her previous experience with the use of energy-based systems and other novel modalities in aesthetic dermatology and plastic surgery. Experience with cosmetic treatments is the most critical element in managing participant risk in this trial. All other known risks will be disclosed to the participant via the informed consent process. Risks have been mitigated by the specific design employed in manufacturing the device.

REPORTING ADVERSE EVENTS AND COMPLICATIONS

Adverse Events

The Investigator is responsible for the detection and documentation of events meeting the criteria and definition of an AE or SAE, as provided in this protocol. During the study when there is a safety evaluation, the Investigator or site staff will be responsible for detecting, documenting, and reporting AEs and SAEs as detailed in this Section of the protocol.

At the treatment and follow-up visits, participants will be assessed for known physiological responses and adverse events.

Adverse Event (AE)

- An adverse event (AE) is defined as any unfavorable or unintended sign, symptom, or disease that occurs or is reported by the participant to have occurred, or a worsening of a pre-existing condition. An adverse event may or may not be related to the study treatment.
- AEs will be elicited through direct questioning and participant reports. Any abnormality in physical examination findings that the investigator believes is clinically significant (CS) to the research participant and that occurred after initiation of the first study treatment will be reported as AEs. Abnormal findings that are NOT clinically significant should not be recorded as an AE.

Adverse Device Effect (ADE)

- An ADE is defined as an adverse event related to the use of an investigational medical device. This definition includes any adverse events resulting from insufficient or inadequate instructions for use, deployment, implantation, installation, or operation, or any malfunction of the investigational medical

device as well as any event resulting from use error or from intentional misuse of the investigational medical device. This includes “comparator” if the comparator is a medical device.

1. Reporting of Adverse Events

- Report initiation for all AEs and SAEs will begin at the time of the first treatment and continue until the end of the final study observation visit. All events will be followed to resolution or until the participant completes the study. A final assessment of outcome will be made at that time.
- All AEs must be recorded in the participant’s medical records and in the case report form. AEs will be reported using customary medical terminology along with the following information: the onset and end dates, whether the event is an SAE, the impact the event had on study treatment, the severity of the event, the causality of the event, whether treatment was given as a result of the event, and the outcome of the event.

2. Impact on Study Treatment

- The impact the event had on the study treatment will be assessed as either: none, study treatment interrupted, study treatment discontinued, or not applicable. The “not applicable” assessment will be used only when the participant is in the observation phase of the protocol.

3. Causality Assessment

- AEs will be assigned a relationship (causality) to the study treatment. The Investigator will be responsible for determining the relationship between an AE and the study treatment. The type of event, organ system affected, and timing of onset of the event will be factors in assessing the likelihood that an AE is related to the study treatment. Relationship of AEs to study treatment will be classified as follows:
 - i. Definitely related: This category applies to those AEs that the Investigator feels are incontrovertibly related to the study treatment. An AE may be assigned an attribution of definitely related if or when it meets all of the following criteria: (1) it follows a reasonable temporal sequence from administration of the study treatment; (2) it could not be reasonably explained by the known characteristics of the participant’s clinical state, environmental or toxic factors, or other modes of therapy administered to the participant; (3) it follows a known response pattern to treatment with the study treatment.
 - ii. Probably related: This category applies to those AEs which, after careful medical consideration at the time they are evaluated, are felt with a high degree of certainty to be related to the study treatment. An AE may be considered probable if or when (must have three): (1) it follows a reasonable temporal sequence from administration of the study treatment. (2) It could not readily have been produced by participant’s clinical state, environmental or toxic factors, or other therapies administered to the participant. (3) Disappears or is decreased upon

discontinuation of the study treatment. (4) It follows a known response pattern to treatment with the study treatment.

- iii. Possibly related: This category applies to those AEs which, after careful medical consideration at the time they are evaluated, are judged unlikely but cannot be ruled out with certainty to the study treatment. An AE may be considered possible if or when (must have two): (1) it follows a reasonable temporal sequence from administration of the study treatment. (2) It could not readily have been produced by participant's clinical state, environmental or toxic factors, or other therapies administered to the participant. (3) Disappears or is decreased upon discontinuation of the study treatment. (4) It follows a known response pattern to treatment with the study treatment.
- iv. Remotely related: In general, this category can be considered applicable to those AEs which, after careful medical consideration at the time they are evaluated, are judged likely to be unrelated to the study treatment. An AE may be considered unlikely if or when (must have two): (1) it does not follow a reasonable temporal sequence from administration of the study treatment. (2) It could not readily have been produced by participant's clinical state, environmental or toxic factors, or other therapies administered to the participant. (3) Disappears or is decreased upon discontinuation of the study treatment. (4) It does not follow a known response pattern to treatment with the study treatment.
- v. Unrelated: This category applies to those AEs which, after careful consideration at the time they are evaluated, are clearly and incontrovertibly due to extraneous causes (disease, environment, etc.) and determined with certainty to have no relationship to the study treatment.

4. Outcome Assessment

- The outcome of the event will be assessed as either: resolved, resolved with sequelae, ongoing, or death. Only one AE per participant is allowed to have an outcome assessment as "death." If there are multiple causes of death for a given participant, only the primary cause of death will have an outcome of death.

5. Serious Adverse Events

- A Serious Adverse Event (SAE) is defined as any AE that:
 - i. Results in death
 - ii. Is life threatening (the participant is at immediate risk of dying from the adverse experience)
 - iii. Requires participant hospitalization or prolongs existing hospitalization
 - iv. Results in persistent or significant disability/incapacity

- v. Is a congenital anomaly/birth defect
- vi. Medical or surgical intervention to prevent life-threatening illness or injury or permanent impairment to a body structure or a body function

6. Reporting SAEs

- o The Investigator is required to report all SAEs that occur from RAP treatment through 30 days post end of study. Once the investigator becomes aware of an SAE, he/she must report the SAE to the Sponsor, ZELTIQ Aesthetics, Inc. ***within 24 hours.***
 - o Contact Information:
 - Email: [REDACTED] and [REDACTED]
 - Phone: [REDACTED]
- o The Sponsor ZELTIQ Aesthetics, Inc. may request additional supporting documentation as it becomes available, such as lab reports, electrocardiogram reports, discharge summary, hospital notes, etc., if applicable. Additional follow-up information as it becomes available must be reported to the same phone number and contact info listed at the beginning of this document.
- o The Investigator is also responsible for reporting all SAEs to the appropriate Institutional Review Board (IRB) in accordance with local laws and regulations. The Investigator is responsible for maintaining documentation in the study file that indicates the IRB has been properly notified.

7. SAE Follow-up

- o All participants experiencing an SAE, including discontinued participants, must be closely followed until sufficient information is obtained to indicate a return to normal status or until the event stabilizes at a level acceptable to the investigator, i.e., recovery, return to baseline status, no further improvement expected, or death.
- o For each SAE indicated as an unresolved event on the initial report, regardless of whether the participant completed the study or withdrew, the site should submit a follow-up report with updated information.

Device Malfunctions

A device deficiency is an inadequacy of a medical device with respect to its identity, quality, durability, reliability, safety, or performance.

Device malfunctions will be monitored and documented by the Sponsor for this study since they will be on-site for all treatments when the device is in use. If a malfunction occurs, reporting will be managed directly by the Sponsor per their Standard Operating Procedures.

STUDY PARTICIPANT INFORMED CONSENT

All eligible participants must sign the informed consent form prior to enrollment in the study. The participant and the Investigator or designee will discuss the benefits and risks of the study and review the participant consent form to ensure the participant understands

the scope of the study. It is the Investigator's or designee's responsibility to ensure that participants understand that participation in the study is voluntary, and that the quality of their medical care will not be adversely affected if they decline to participate in the study. Adequate time for any questions and explanations will be provided. Participant will have the opportunity to discuss the study with their surrogates and have time to think about it prior to participating. Participants may withdraw their consent at any time throughout the course of treatment. Once the participant understands the informed consent, he/she will be allowed to voluntarily agree to participate by signing the document. The investigator/designee is responsible for obtaining informed consent prior to enrollment in the study and ensuring that participant have a copy of the document for their records. The participant is considered enrolled in the study after the informed consent has been signed and it has been verified that the participant meets all inclusion criteria and none of the exclusion criteria.

RECORDS MANAGEMENT

Study Records Retention: Each site will maintain appropriate medical records for this study in accordance with institutional requirements including, but not limited to, hospital records, laboratory tests, pharmacy dispensing records, x-rays, and clinical charts. As part of study participation, each site will permit the Sponsor ZELTIQ Aesthetics, Inc., or its designee, to examine (and when required by applicable law, to copy) clinical records for the purposes of quality assurance reviews, audits and evaluation of study safety and progress.

- i. Essential documents, as listed below, must be retained by the site until at least 2 years after completion or termination of the investigation, or longer if advised by the Sponsor or designee.
- ii. If the Investigator relocates, retires, or for any reason cannot keep study records, the records may be transferred to an acceptable designee. The Sponsor or its designee must be notified in writing of the name, address, and telephone number of the person designated to retain the study records. By signing the protocol, the Investigator agrees to adhere to the document retention procedures.
- iii. Essential documents may include:
 1. IRB approvals for the study protocol and all amendments
 2. Participant's informed consent forms
 3. All source documents
 4. Case Report Forms
 5. Data change forms or data queries
 6. Monitoring logs and appointment schedules
 7. Investigators CVs, medical license information, and financial disclosure documentation

8. All sponsor representative/investigator correspondence, including telephone logs
9. Any other pertinent study documents

Protocol Deviations: Protocol deviations occur when there are variations in the approved study protocol, criteria, or procedure. An example of this would be a participant visit conducted outside the follow-up schedule. As protocol deviations may increase the risk or decrease the benefit of the intervention and/or affect the participant's rights, safety, welfare and/or integrity of the resultant data, investigators are required to record and report all incidences in a deviation log for adjudication during data analysis.

- iv. All protocol deviations must be reported to Sponsor in a timely manner of their occurrence. Evaluation of the deviation and its impact on the study protocol will be adjudicated on a case-by-case basis. Data discrepancies or questions resulting from reported protocol deviations will be managed between Sponsor and the site investigator or their designee.

Protocol Violation: A violation is any non-adherence to the protocol that may result in significant additional risk to the participant (e.g., enrollment of a participant who does not meet the study criteria). A protocol violation can also be an event of non-adherence to GCPs that may impact participant safety (e.g., failure to obtain proper consent before performing study procedures). Violations should be reported to the study sponsor and the IRB within 5 working days if they occur.

INVESTIGATIONAL DEVICE ACCOUNTABILITY AND STORAGE

The Sponsor will maintain full device accountability. The Investigator will maintain adequate records documenting all materials received and returned, and shipping information of the device. All used materials will be discarded by the Investigator after each treatment has been completed.

REGULATORY AND ETHICAL COMPLIANCE

1. The Study will comply with all instructions, regulations, and agreements in this protocol. In addition, the study will comply with all local regulations, external standards and applicable ICH and Good Clinical Practice (GCP) guidelines.
2. Institutional Review Board: The site that is participating in this study must have this protocol and the associated informed consent approved through the IRB. Any amendments to the protocol or informed consent will be routed through IRB for approval prior to use.
3. Participant Confidentiality: Participant confidentiality for all data collected during the course of treatment will be maintained by the Investigator, on-site staff, and the Sponsor. All pictures of the participant's test areas will be de-identified, secure, privileged, and compliant with all HIPAA guidelines. A unique participant identification (ID) code will be assigned to each participant in the study. This ID code will be used throughout the course of treatment to ensure that no identifying

information exists on any Case Report Forms. The document which contains the participant ID key will be stored in a locked cabinet and will only be accessible by authorized study personnel. Private and confidential information about each participant will be preserved in any report or publication of the clinical investigation data.

4. Investigator Conflict of Interest: The proposed study will be conducted in accordance with signed investigator statements.
5. Funding Source: Funding for this study is provided by ZELTIQ Aesthetics, Inc.
6. Changes to Final Protocol: ZELTIQ Aesthetics, Inc. may amend the protocol at any time. All protocol modifications that could potentially affect data collection practices, study scope, participant safety, or scientific quality will be submitted to the IRB for approval prior to implementing the changes.

QUALITY ASSURANCE AND MONITORING

All participant data will be entered into a study database created and controlled by ZELTIQ Aesthetics, Inc.

The Sponsor will train the study site and be present at the initiation of treatment. The Sponsor will monitor the site at various intervals during the study. Monitoring activities may be on site or remote. Case Report Forms and source documents will be reviewed to verify adherence to the protocol; for completeness, accuracy, and consistency of data; and adhere to local regulations on the conduct of clinical research. The Sponsor will collect data throughout the study and at the end of the follow up period.

The investigational site will provide direct access to all trial-related site's source data/documents, and reports for the purpose of monitoring and auditing by ZELTIQ Aesthetics, Inc. or designee, and inspection by local and regulatory authorities (as appropriate).

The investigational site will have established standard operating procedures (SOPs) for quality management. Data will be evaluated for compliance with the protocol and accuracy in relation to source documents. The study will be conducted in accordance with procedures identified in the protocol.

The data and any research conducted will be controlled by ZELTIQ Aesthetics, Inc.

STUDY RESULTS/ANALYSIS

Sample Size Determination: Up to fifteen (15) participants will be enrolled and treated in this study. The sample size is based on clinical and practical exploratory considerations and not a formal statistical power.

Demographics and Baseline Characteristics: Demographic and baseline characteristics will include age, sex, ethnicity, race, gender identity, height, and weight, Fitzpatrick Skin Type, and Cellulite Dimple assessment of bilateral posterior thighs and/or buttocks.

Study Analysis Populations: The Full Analysis Set (FAS) will include all participants who meet all the inclusion and none of the exclusion criteria, received assigned three treatments with the device and completed the 12-week, follow-up visits per the protocol. The FAS will be treated as the primary analysis set.

Effectiveness Parameter Analysis: Descriptive statistics will be performed on the population per protocol, all participants completing the study without major protocol deviations. Descriptive statistics (i.e., mean, standard deviation, etc.) will be provided for all continuous variables, percentages and frequencies for all categorical variables collected in this study.

Summary tables will be used to present population characteristics at Baseline. For categorical parameters, the number and percentage of participants in each category will be presented. The denominator for percentage will be based on the number of participants appropriate for the purpose of analysis. For continuous parameters, descriptive statistics will include n (number of participants), mean, standard deviation, median, and range. No imputation will be used to account for missing data. No processing for outliers will be performed. Data will be presented as reported on the CRF. [REDACTED]

Safety Analysis: The Safety Analysis Set will consist of all enrolled participants who receive RAP treatment (started or completed).

Safety analyses will be performed in terms of incidence and severity of adverse events. These will be tabulated and a complete listing of all reports of adverse and/or unanticipated events will be presented.

SUSPENSION OR PREMATURE TERMINATION OF STUDY

The Sponsor reserves the right to suspend or prematurely terminate the study in its entirety or at an investigational site for significant and documented reasons. An Investigator, IRB, or regulatory authority may suspend or prematurely terminate participation in the clinical investigation for which they are responsible at any time in collaboration with the Sponsor.

PUBLICATION POLICY

Any investigator who wishes to develop a publication or presentation based on the results from this study must obtain written approval from ZELTIQ Aesthetics, Inc. prior to submission. ZELTIQ Aesthetics, Inc. may grant the investigator the freedom to publish any scientific or medical results deemed by the author to be of medical or scientific significance, provided that the information is scientifically sound, does not duplicate a previous or already planned publication, and is not being released prematurely.

STUDY COMPLETION

The IRB must be notified of completion of this study.

REFERENCES

- [1] M. P. Christman, D. Belkin, R. G. Geronemus and J. A. Brauer, "An anatomical approach to evaluating and treating cellulite," *J Drugs Dermatol* , vol. 16, no. 1, pp. 58-61, 2017.
- [2] M. Lokhandwalla, J. A. McAteer, J. C. Williams and B. Sturtevant, "Mechanical haemolysis in shock wave lithotripsy (SWL): II. In vitro cell lysis due to shear," *Phys. Med. Biol.* , vol. 46, p. 1245–1264, 2001.
- [3] J. B. Freund, T. Colonius and A. P. Evan, "A cumulative shear mechanism for tissue damage initiation in shock-wave lithotripsy," *Ultrasound Med Biol.* , vol. 33, no. 9, pp. 1495-1503, September 2007.
- [4] D. Howard and B. Sturtevant, "In vitro study of the mechanical effects of shock-wave lithotripsy," *Ultrasound in Med. & Biol.* , vol. 23, no. 7, pp. 1017-1122, 1997.
- [5] H. Jookaki and M. V. Panzer, "Skin mechanical properties and modeling: A review," *Proc IMechE Part H: J Engineering in Medicine*, 2018.
- [6] D. Hexsel, S. Fabi, G. Sattler, R. Bartsch and e. al, "Validated assessment scales for cellulite dimples on the buttocks and thighs in female patients," *Dermatologic Surgery*, 2019.
